15.2 GUIDELINES AND DEFINITIONS FOR RECORDING ADVERSE EVENTS

The Investigator or a designated member of his/her staff will probe each subject for any AEs that may have occurred. The Investigator should always ask the same question when conducting the verbal probe in order to ensure uniformity between subjects. The Investigator should ask:

"How are you doing (feeling)?"

Based on the subject's response to this question, the Investigator should ask additional questions relevant to the specific complaint such as:

"How severe is/was the symptom?"

"How often did the symptom occur?"

"How long did the symptom last?"

It is the Investigator's responsibility to review the results of all diagnostic and laboratory tests as they become available and ascertain if there is a clinically significant change from baseline. If the results are determined to be a clinically significant change from baseline, this should be reported as an AE. The Investigator may repeat the diagnostic procedure or laboratory test or request additional tests to verify the results of the original tests. When possible, a diagnosis associated with the abnormality should be used as the reported AE.

Using provided definitions, the Investigator will then:

(1) rate the intensity and seriousness of the AE, (2) estimate the causality of the AE to study drug, and (3) note actions taken to counteract the AE.

Definitions of Intensity, Seriousness, Causality, Action Taken, and Outcome

INTENSITY

An assessment of the relative intensity (severity) of an AE is based on the Investigator's clinical judgment. The maximum intensity encountered during the evaluation period should be checked. The assessment of intensity should be independent of the assessment of the seriousness of the AE.

SERIOUSNESS

An SAE is one that represents an actual or potential significant hazard. This includes, but is not limited to, an event that is fatal, life-threatening, permanently or severely disabling, requires or prolongs inpatient hospitalization, is a congenital abnormality (offspring of subject), or is medically significant (important medical events that may not result in death, be life-threatening, or require hospitalization may be considered an SAE when, based upon appropriate medical judgment, they may jeopardize the subject and may require medical or surgical intervention to prevent 1 of the outcomes listed in this definition).

Hospitalizations that would not be considered SAEs include those for:

- Routine treatment or monitoring of the study indication not associated with any deterioration in condition (eg, hospitalization for a routine right heart catheterization).
- Treatment which was elective or pre-planned, for a pre-existing condition not associated with any deterioration in condition (eg, pre-planned operation which does not lead to further complications, etc).
- Treatment of an emergency, in an outpatient setting for an event not fulfilling any of the definitions of serious as given above and not resulting in hospital admission.

CAUSALITY

An estimate of causality between a specified AE and the study drug is made by the Investigator. Several factors should be considered when determining causality. These factors include temporal relationship and response to withdrawal or reintroduction of the study drug.

Definitions of the causality categories are as follows:

- NOT RELATED There is not a temporal relationship to study drug administration (too early, or late, or study drug not taken), or there is a reasonable causal relationship between another drug, or concurrent disease and the SAE, or any of the following:
 - An event that precedes the first administration of study drug
 - An event for which the cause is clearly related to an external event
 - Temporal relationship to study drug is atypical
 - Is readily explained by an intercurrent illness AND has an expected level of severity, duration, and resolution
 - An alternative explanation (concomitant drug, intercurrent illness) is likely
- POSSIBLE There is a reasonable causal relationship between the study drug and the SAE. Dechallenge information is lacking or unclear, study drug administration was not modified in response to the SAE, or any of the following:

- Has a reasonable temporal relationship to study drug
- The event has a plausible biological link to the activity of the study drug
- Is unlikely to be related to an intercurrent illness or has an unexpected degree of severity, duration, or complication
- PROBABLE There is a reasonable causal relationship between the study drug and the SAE. The event responds to dechallenge—the event resolves or improves with modification of study drug administration. Rechallenge (the original study drug was restarted) is not required, or any of the following:
 - Has a reasonable temporal relationship to study drug
 - The event has a plausible biologic link to the activity of the study drug
 - Not readily explained by an intercurrent illness
 - Not readily explained by external event
 - Improves on discontinuation of study drug
 - If study drug has been discontinued, may recur or reintroduction of study drug

ACTION TAKEN

STUDY DRUG DOSE MODIFICATION*

- Dose Not Changed The dose or regimen of the study drug was not changed.
- Dose Increased The dose or regimen of study drug was increased.
- Dose Decreased The dose or regimen of study drug was decreased.
- Drug Interrupted Administration of the study drug was stopped temporarily.
- Drug Withdrawn Administration of the study drug was stopped permanently and not restarted.
- Unknown Changes to the administration of the study drug cannot be determined.
- Not Applicable

NOTE: Only the last study drug action should be recorded in the eCRF. For example, if the study drug is withdrawn and then the decision is made to restart, the dose modification of "Drug interrupted" should be reported on the SAE form.

OUTCOME

- Fatal The study subject died.
- Not Recovered/Not Resolved The AE was ongoing at the time of death or at the time the subject was lost to follow up.
- Recovered/Resolved The AE resolved.
- Recovered/Resolved with Sequelae The AE is considered resolved; however, there is residual sequelae. Some events do not return to baseline, such as metastasis or progression of disease; however, once these events are determined by the Investigator to

be stable or chronic, the Investigator may consider the event to be resolved or resolved with sequelae.

- Recovering/Resolving The AE is improving but is not yet completely recovered/resolved.
- Unknown The outcome of the AE cannot be determined.

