7.6.2 TreT Dose Titration Visits

Dose titration will be encouraged during the Optional Extension Phase; the dose of TreT should be titrated upward, as clinically tolerated, to identify a maximum stable dose in each subject. Titration may occur at a scheduled Extension Visit, or may occur at an unscheduled visit as deemed clinically appropriate by the Investigator.

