#### 12.1 EXTENT OF EXPOSURE

All study drug dosing will be listed for all subjects. The listing will include TreT dose (in mcg), date of first dose, and date of last dose. The duration of exposure and TreT dose during the Treatment Phase and during the Optional Extension Phase will be summarized by assigned TreT dose and overall.

For study treatment compliance, the number and percentage of days with at least 1 dose of TreT will be calculated and summarized by TreT dose and overall for both the Treatment Phase and Optional Extension Phase. Additionally, for each subject, compliance will be calculated as (Total number of doses taken divided by total number of doses supposed to be taken) times 100% and summarized by TreT dose and overall for both the Treatment Phase and Optional Extension Phase.

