# 15 APPENDICES

# 15.1 LIST OF TABLES

Table Number	Table Title
14.1.1	Summary of Subject Accountability
14.1.2	Summary of TreT Exposure
14.1.3.1	Summary of Entry Criteria Violations
14.1.3.2	Summary of Protocol Deviations
14.1.4	Summary of Demographics
14.1.4.1	Summary of Demographics by Time of Enrollment
14.1.5	Summary of Medical History
14.1.6	Summary of PAH History
14.1.6.1	Summary of PAH History by Time of Enrollment
14.1.7.1	Summary of Concomitant Medications Ongoing at Baseline
14.1.7.2	Summary of Concomitant Medications Added during the Treatment Phase
14.1.7.3	Summary of Concomitant Medications Added during the Optional Extension Phase
14.1.7.4	Summary of Background PAH Medications
14.1.7.5	Summary of Tyvaso Medication History
14.1.8	Summary of TreT Dosing
14.1.9	Summary of TreT Treatment Compliance
14.2.1.1	Summary and Analysis of 6MWD (meter) during Treatment Phase
14.2.1.2	Summary of 6MWD (meter) during Optional Extension Phase
14.2.2.1	Summary of Preference Questionnaire for Inhaled Treprostinil Devices
14.2.2.2	Analysis of Preference Questionnaire for Inhaled Treprostinil Devices
14.2.3	Summary and Analysis of PAH-SYMPACT Questionnaire
14.3.1.1	Overall Summary of Adverse Events
14.3.1.2	Summary of Adverse Events by System Organ Class and Preferred Term
14.3.1.3	Summary of Adverse Events by Preferred Term
14.3.1.4	Summary of Deaths
14.3.1.5	Summary of Serious Adverse Events by System Organ Class and Preferred Term
14.3.1.6	Summary of Non-serious Adverse Events by System Organ Class and Preferred Term
14.3.1.7	Summary of Adverse Events Probably or Possibly Related to Study Drug by System Organ Class and Preferred Term
14.3.1.8	Summary of Adverse Events Leading to Permanent Discontinuation of Study Drug by Preferred Term
14.3.1.9	Summary of Adverse Events by System Organ Class, Preferred Term, and Severity
14.3.1.10	Listing of Deaths
14.3.1.11	Listing of Serious Adverse Events

Table Number	Table Title
14.3.1.12	Summary of Adverse Events by System Organ Class, Preferred Term, and Time of Enrollment
14.3.2.1	Summary of Clinical Chemistry
14.3.2.2	Summary of Clinical Chemistry Shift from Baseline
14.3.2.3	Summary of Hematology
14.3.2.4	Summary of Hematology Shift from Baseline
14.3.3.1	Summary of Vital Signs
14.3.3.2	Summary of Electrocardiogram Parameters
14.3.3.3	Summary of Electrocardiogram Categorical Results

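### Recording only the last study drug action for an AE can lose the link between that AE and a dose reduction or interruption, and the SAP plans no table of such AEs

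*Protocol*

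**What the plan says.** Under Action Taken, Protocol Appendix 15.2 gives separate codes, among them *Dose Decreased* ("The dose or regimen of study drug was decreased"). The others are *Dose Not Changed*, *Dose Increased*, *Drug Interrupted*, *Drug Withdrawn*, *Unknown* and *Not Applicable*. A note then sets the recording rule: "Only the last study drug action should be recorded in the eCRF". Its single example takes the case "if the study drug is withdrawn and then the decision is made to restart", and says that *Drug Interrupted* "should be reported on the SAE form". No example covers a decrease followed by an increase, or an interruption followed by restart at another dose.

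For the Optional Extension Phase, Protocol 7.6.2 says that "the dose of TreT should be titrated upward, as clinically tolerated, to identify a maximum stable dose in each subject". Section 6.1.2 places the earliest titration at the Week 3 Visit, after that visit's assessments.

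SAP 12.1 describes the dosing listing: "The listing will include TreT dose (in mcg), date of first dose, and date of last dose". SAP 12.2 has the AE listing reproduce what the eCRF holds. The only AE output it defines by action taken is for discontinuation, which appears in SAP 15.1 as Table 14.3.1.8: "Summary of Adverse Events Leading to Permanent Discontinuation of Study Drug by Preferred Term".

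**The concern.** The primary objective is safety and tolerability, and long-term tolerability in the extension is a secondary one. There is no control group and the planned size is 45 subjects. Subjects enter already stable on inhaled treprostinil, so tolerability problems may well show as dose reductions or pauses as well as permanent stops. If the AE record keeps only the final dose action, a reduction made for an AE can be replaced by a later, unrelated titration step. The AE would then look as if it had needed no reduction. Any such loss makes tolerability look better, never worse.

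The rule also sits oddly beside its neighbours in the same appendix. For intensity, the investigator keeps the highest level reached. For a *Probable* causality rating, improvement after the study drug was modified is part of the evidence. Overwriting the modification removes the recorded action behind that rating.

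**Working it through.** No arithmetic applies: the plan gives no figure on this point, and the sample size of 45 is stated not to come from a calculation (Protocol 10.2). The check is to trace dose-action sequences through the rule in Appendix 15.2 and see what each leaves in the AE record.

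| Actions during one AE | Code under the literal rule | What the AE record loses |
|---|---|---|
| Decrease only | Dose Decreased | Nothing |
| Permanent withdrawal only | Drug Withdrawn | Nothing |
| Withdrawal, then restart | Drug Interrupted (by the example) | Nothing |
| Decrease, then permanent withdrawal | Drug Withdrawn | The earlier decrease; the more serious action is kept |
| Interruption, then restart at a lower dose | Dose Decreased | The interruption |
| Decrease, then re-titration upward | Dose Increased | The decrease |

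The loss is therefore confined to AEs with more than one dose action. In the last two rows the example does not settle the code. Taken strictly, the last action in the example is a restart, yet the code chosen describes the temporary stop. A site following the sentence and a site following the logic of the example could code the same course differently.

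Next, can the missing action be recovered from other planned data?

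- **Dosing diary** (Protocol 6.2): dosing is recorded from Baseline to the end of study, separately from the AE page.
- **Dosing listing and Table 14.1.8** (SAP 12.1 and 15.1): doses with dates, and a summary of dose for both phases. A change of dose should be visible. No reason for the change and no AE link is named.
- **Compliance, Table 14.1.9**: days with at least one dose, and doses taken against doses due. A pause may show here, without a cause.
- **Extension exposure**: SAP 1.2.6 makes no adjustment for interruptions and assumes continuous treatment, so exposure duration need not reveal a pause.
- **AE listing** (SAP 12.2): shows the action the eCRF stored, hence the last one if the rule was followed.

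Dose changes themselves should therefore be recoverable. The stated link from a given AE to a given reduction or interruption may not be, except by comparing AE dates with dose dates.

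Last, the phase. One dose is assigned for the 3-week Treatment Phase (Protocol Table 6-1), and up-titration belongs to the extension. Decrease followed by re-titration is thus foreseeable mainly there. The missing SAP table is a separate gap: it affects both phases and remains even if every code is stored well.

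**The case against.** The strongest reply is that Appendix 15.2 asks the investigator to note what was done to counter the AE. A later increase made as routine titration does not counter anything, so the last relevant action would still be *Dose Decreased*. The example points the same way: restarting the drug does not erase the stop. This stands to the extent that storage as *Dose Increased* is one reading and not a certainty. It does not remove the problem, because the note itself refers to the last study drug action without that restriction.

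A reader might infer that tolerability-driven reductions disappear from the primary safety data, or that every reversed reduction is misclassified. The documents do not support this. The AE is recorded with its dates, intensity, seriousness, relationship and outcome (Protocol 9.2). Unreversed reductions and permanent discontinuations keep their codes, and dosing is listed and summarised separately. The overwriting concerns mainly the extension, where tolerability is a secondary objective.

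It may also be said that the dosing fields named in SAP 12.1 need not be exhaustive, since SAP 9 lists everything collected in the eCRF. That is fair. The eCRF is not in the documents, and a reason-for-change field there would reduce the problem.

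**Conclusion.** The point holds as a limited loss of information plus a reporting gap. The recording rule can remove, from the AE record, the attribution of a dose reduction or interruption to an AE when another dose action follows, and the rule and its example can lead sites to different codes. Separately, no planned table shows AEs leading to reduction or interruption in either phase, so even well-coded actions would reach the reader only through listings.

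The size cannot be derived. A reader might try assumed rates: if 10% to 30% of 45 subjects reduced the dose for an AE (45 × 0.10 = 4.5; 45 × 0.30 = 13.5) and half were re-titrated, about 2 to 7 would be affected. Neither rate has a source in the documents, the extension is optional so 45 is not its denominator, and the sum takes every such case to be miscoded. It should not be cited as an estimate.

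The conclusion assumes that sites apply the note as written and that the eCRF has no field linking dose changes to AEs. It is worth correcting because the bias runs one way and the correction is cheap.

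**What to change.** These changes concern recording and reporting only; they do not touch dosing.

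1. In Appendix 15.2 and the eCRF completion guide, replace the last-action sentence. Record for each AE the most restrictive action taken in response to that AE over its whole course, in the order: *Drug Withdrawn* (if never restarted), *Drug Interrupted*, *Dose Decreased*, *Dose Not Changed*. Recording all such actions is the alternative and loses nothing; with one code, an interruption followed by restart at a lower dose would still show only the interruption.
2. Keep the existing example. Keep *Dose Increased* only where the increase was itself the response to the AE, and keep *Unknown* and *Not Applicable*. Enter later re-titration only in the dosing record.
3. In SAP 12.2 and 15.1, add one table of AEs leading to dose decrease or interruption, for the Treatment Phase and for the combined phases.
4. Check whether the eCRF already holds a reason for dose change. If it does, use it to support the new table and to limit queries.

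Cost: one changed sentence, one more table, and queries on entries already made under the present rule. The reported tolerability figures may become slightly less favourable.

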#### ABBREVIATIONS AND DEFINITIONS

6MWD 6-Minute Walk Distance 6MWT 6-Minute Walk Test

AE Adverse event

ATC Anatomical Therapeutic Chemical

BMI Body mass index ECG Electrocardiogram

eCRF Electronic Case Report Form ERA Endothelin receptor antagonist

FC Functional Class

HR Heart rate

IRT Interactive Response Technology

MedDRA Medical Dictionary for Regulatory Activities

PAH Pulmonary arterial hypertension

PAH-SYMPACT Pulmonary Arterial Hypertension-Symptoms and Impact

PDE5-I Phosphodiesterase type 5 inhibitor

PK Pharmacokinetic(s)

PQ-ITD Preference Questionnaire for Inhaled Treprostinil Devices

PT Preferred term
QID Four times daily

QT interval corrected for heart rate

SAE Serious adverse event
SAP Statistical Analysis Plan
sGC Soluble guanylate cyclase

SOC System organ class

TreT Treprostinil Inhalation Powder WHO World Health Organization

#### 1 PREFACE

This plan provides further details of the planned analyses for the TIP-PH-101 study as presented in the study protocol. Additional post hoc or unplanned analyses that are not defined in this Statistical Analysis Plan (SAP) may be performed. Such analyses will be documented in the clinical study report.

#### 1.1 CHANGES TO STATISTICAL ANALYSIS PLAN

The following changes have been made to the SAP:

- Addition of accommodations for COVID-19 pandemic including additional summary tables
- Minor changes to visit timing due to protocol amendment
- Adjustments to visit windows due to protocol amendment
- Removal of Optional Extension Phase summaries for demographics and baseline characteristics, medical history, pulmonary arterial hypertension (PAH) history, and concomitant medications
- Modification of background therapy listing and summary
- Removal of oxygen assessments from 6-minute walk listing since these data were not collected

### 1.2 COVID-19 ACCOMMODATIONS

The COVID-19 pandemic is expected to have various effects on clinical trials. Due to closure of sites during the COVID-19 pandemic, it is expected that there will be more missing data than usual, more protocol deviations may be observed, changes in patient population may occur, adverse events and concomitant medications may be underreported, and/or treatment interruption may occur. Twenty subjects were enrolled prior to enrollment hold/closures at sites due to the pandemic. These subjects will comprise the pre-pandemic subjects. All other subjects enrolled later will comprise the post-pandemic subjects.

# 1.2.1 Missing Data

It is known that 3 subjects were unable to provide pharmacokinetic (PK) assessments at the Treatment Phase Week 3 Visit. All other subjects had completed the Treatment Phase Week 3 Visit prior to site closures, and no new subjects were enrolled during the time of site closures. Subjects were unable to attend visits during the Optional Extension Phase. Visit windows will be expanded to allow for out-of-window visits to be slotted to a scheduled visit.

#### 1.2.2 Protocol Deviations

Protocol deviations are reviewed periodically, at data cutoff, and at the end of the study. No per-protocol analyses were planned for this study, so no modifications to the analyses due to protocol deviations will be done.

# 1.2.3 Patient Population Characteristics

In order to assess whether changes in the population characteristics have occurred, separate demographics and baseline characteristic summaries will be created based on enrollment pre- or post-pandemic.

# 1.2.4 Impact on Safety Evaluation

In order to assess whether adverse events (AEs) were underreported during site closures, the rate of AEs will be calculated pre- and post-pandemic for those subjects who remained in the study during site closures. No assessment of underreporting of concomitant medications is planned.

# 1.2.5 Impact on PK Evaluation

Only 3 subjects were unable to provide PK assessments at the Treatment Phase Week 3 Visit due to the pandemic. This will result in a smaller PK population, but there are no planned changes to the analyses.

#### **1.2.6** Treatment Interruptions

Since the extension phase is optional, no modifications will be made for treatment interruptions. The assumption that subjects were on treatment throughout is conservative.

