#### 12.2 ADVERSE EVENTS

All AEs will be coded to the appropriate PT and SOC using MedDRA. AEs will be listed by TreT dose including all details recorded on the eCRF plus an indicator of whether the event was treatment emergent. Treatment-emergent AEs are those AEs with an onset date equal to or after the start date of TreT. The AE listings will include the AE verbatim term and its corresponding PT and SOC.

The AE summaries will be limited to include only treatment-emergent AEs and will be prepared for the Treatment Phase and the combined Treatment Phase and Optional Extension Phase. The non-treatment-emergent AEs (the AEs occur after signing the Informed Consent Form but before receiving TreT) will be listed but not included in summary tables.

All summaries will include the number and percentage of subjects experiencing each type of AE and the total number of each type of AE, in order of overall frequency and/or SOC. Serious adverse events (SAEs) and non-serious AEs will also be summarized by SOC and PT.

The total number of AEs and the AE rates will be calculated and summarized for each display, as appropriate. The AE rate will be calculated as the total number of AEs divided by the total patient years of exposure to study drug per TreT dose.

AEs possibly or probably related to study drug will be summarized. An AE summary by severity (mild, moderate, and severe) will also be provided.

Separate listings and summary tables will be provided for all SAEs, AEs leading to the discontinuation of study drug, and all deaths during the study (if data permit). For the listing

of deaths, information for all subjects who die during the study period from Baseline to the end of the study (including 30 days after the last TreT dose) will be included.

To assess possible underreporting of AEs, an additional summary will be created for AEs by time of enrollment: pre- or post-pandemic.

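### The check for AE underreporting is tabulated by enrollment date, so it cannot show the site-closure period; a lesser point is that calling the treatment-interruption assumption conservative is unsupported for AE rates

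*SAP*

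**What the plan says.** **Underreporting check.** SAP 1.2 expects that site closures may lead to underreported AEs. SAP 1.2.4 states the response: "the rate of AEs will be calculated pre- and post-pandemic for those subjects who remained in the study during site closures". SAP 12.2 describes the output differently: "To assess possible underreporting of AEs, an additional summary will be created for AEs by time of enrollment: pre- or post-pandemic". The matching entry in SAP 15.1 is Table 14.3.1.12, "Summary of Adverse Events by System Organ Class, Preferred Term, and Time of Enrollment". SAP 1.2 defines the two groups: the 20 subjects enrolled before the hold are pre-pandemic and all later ones are post-pandemic. SAP 1.2.1 adds that enrollment stopped while sites were closed.

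**Interruptions.** SAP 1.2.6 says that "no modifications will be made for treatment interruptions", giving as its reason that the extension is optional, and then adds "The assumption that subjects were on treatment throughout is conservative".

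**AE measures.** SAP 12.2 reports counts, percentages of subjects and a rate. The rate is the "total number of AEs divided by the total patient years of exposure to study drug per TreT dose". The numerator rule is "Treatment-emergent AEs are those AEs with an onset date equal to or after the start date of TreT". Summaries are "prepared for the Treatment Phase and the combined Treatment Phase and Optional Extension Phase". SAP 12.1 lists first and last dose dates and summarizes duration of exposure, without saying whether gaps are removed.

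**The concern.** A check for underreporting during a period has to compare that period with other time. A split by enrollment date compares groups of people instead. If the table is produced as specified, similar columns could be read as reassurance about AE capture during closures, although the table holds no information on that question.

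The interruption sentence is a separate matter. It attaches a direction of bias to an assumption without naming the outcome to which it applies. Long-term safety and tolerability is a secondary objective, and the AE rate is the planned AE measure that allows for unequal follow-up in the extension. A reader who sees the word conservative would take the rate to be, if anything, too high. The two issues meet in one place. If interruptions fell within the closures and those days count as exposure, the closure-period rate could fall for a reason other than underreporting.

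**Working it through.** The documents give no figure to reproduce for either part.

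**Part 1: the two descriptions side by side**

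- SAP 1.2.4: the population is subjects in the study during closures; the contrast is between periods.
- SAP 12.2 and Table 14.3.1.12: no such restriction is stated; the contrast is between enrollment groups.

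Step 1. Anyone in the study during closures enrolled either before or during them. Nobody enrolled during them, so all such subjects are among the first 20.

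Step 2. Of the planned 45, the later group is 45 − 20 = 25. None of them contributes time during the closures.

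Step 3. Restricted to the SAP 1.2.4 population, the post-pandemic enrollment column is empty. Without that restriction, the table compares different people with different lengths of follow-up. The pre-pandemic column pools time before, during and after closures.

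Step 4. No other table in SAP 15.1 is titled for a comparison by period.

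No numerical assumption is needed.

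**Part 2: the interruption assumption**

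*Counts and percentages.* Any AE with onset on or after TreT start counts, and the percentage denominator is the Safety Population (SAP 8). Interruption dates enter neither, so the assumption changes nothing under the SAP's own rule.

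*Rate.* Let f be the share of counted time off drug, and q the off-drug AE rate divided by the on-drug rate. If gaps stay in the denominator:

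reported rate / on-drug rate = (1 − f) + f·q = 1 − f(1 − q)

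This is below 1 if q < 1, equal to 1 if q = 1, and above 1 if q > 1.

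*Scale.* The documents give neither f nor q. All of the following are assumptions: 6-week gaps in 10 or in all 20 of the pre-closure subjects, no other gaps, and two follow-up patterns.

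- First database lock, with 52 weeks for 20 subjects and 12 weeks for 25: 20×52 + 25×12 = 1340 subject-weeks.
- All 45 subjects followed for 52 weeks: 45×52 = 2340 subject-weeks.

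| Follow-up | Subjects with gap | f | Ratio, q = 0.5 | Ratio, q = 1.5 |
|---|---|---|---|---|
| 1340 weeks | 10 | 60/1340 = 4.5% | 0.978 | 1.022 |
| 1340 weeks | 20 | 120/1340 = 9.0% | 0.955 | 1.045 |
| 2340 weeks | 10 | 60/2340 = 2.6% | 0.987 | 1.013 |
| 2340 weeks | 20 | 120/2340 = 5.1% | 0.974 | 1.026 |

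*Comparison with chance.* The approximate 95% Poisson error of a rate is 1.96/√(number of AEs). For 100 AEs it is 1.96/10 = ±20%; for 225 AEs it is 1.96/15 = ±13%. These event numbers are also illustrative. Rates are planned per TreT dose, so the error within a dose is larger than for all subjects together.

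**The case against.** **On the check.** SAP 12.2 calls the enrollment table additional, so the SAP 1.2.4 rates might still be produced. That is possible. However, SAP 12.2 names underreporting as the purpose of the enrollment table, and the table list contains nothing else for it. Telephone or email contact between visits (Protocol 3.3.2.8 and 7.7) also helps AE capture during closures. That lowers the risk of underreporting but does not make the table able to detect it. A reader might infer that AEs were in fact underreported. The SAP says only that they may have been.

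**On interruptions.** The opposing case is strong on size.

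- Patient-years of exposure to study drug could literally exclude off-drug days. That gaps are counted is an inference, though the natural one from SAP 1.2.6.
- SAP 12.1 already plans the percentage of days with at least one dose and a compliance figure for the extension, so readers will see roughly how much time was off drug.
- SAP 1.2.1 says that visits were missed, not that TreT was stopped.
- The study has one arm, and SAP 12.2 plans no test on AE rates.

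A reader might infer a substantial understatement of the AE rate. The documents do not support that. They do not say whether q is below 1. For f to reach 20%, closure-related gaps would need 0.20×1340 = 268 subject-weeks, or 268/20 = 13.4 weeks off drug in every one of the 20 subjects. With 2340 subject-weeks, it would need 468/20 = 23.4 weeks each. A reader might also take the assumption as truly conservative for counts and percentages. It is neutral there.

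**Conclusion.** The underreporting check is wrong as specified: the table and its stated purpose do not match. This rests only on the SAP's enrollment-group definition and its statement that nobody enrolled during closures.

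The point on SAP 1.2.6 is minor. The claim has no stated outcome, no effect on counts or percentages, and no fixed direction for the rate. Under the assumed gaps and q = 0.5, the rate would be 1.3% to 4.5% low; at q = 1.5 it would be 1.3% to 4.5% high. Both are well inside chance variation. The defect is an unsupported label and an undefined denominator, not a demonstrated bias. The Treatment Phase summaries are little affected: according to SAP 1.2.1, all but 3 of the subjects then enrolled had completed Week 3 before the closures.

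**What to change.** 1. Replace or supplement Table 14.3.1.12 with AE rates per patient-year by calendar period (before, during and after closures), within subjects who were in the study during closures. Align the SAP 12.2 text with SAP 1.2.4. AE onset dates and exposure dates are already collected; the closure dates that define the periods must be stated. The cost is one table. Limits: about 20 subjects at most, and period is tied to time on TreT, so the result is descriptive.
2. Delete the conservative claim from SAP 1.2.6, and state in SAP 12.1 or 12.2 whether interruption days count in patient-years. Use the same rule in the period table. The cost is wording only.
3. Optional: for the extension, add one sensitivity rate that removes documented interruption days from the denominator and AEs with onset on those days from the numerator. List those AEs separately, and do not count blank diary days as interruptions. Both parts must be matched: all AEs over on-drug time alone would overstate the on-drug rate by the factor 1 + f·q/(1 − f), which at f = 9.0% and q = 0.5 is 1 + 0.045/0.910 = 1.049. The cost is one extra table and a listing. Interruption dates will be incomplete, because they rest largely on dosing diaries (Protocol 6.2) and on an action-taken field that keeps only the last action (Protocol 15.2).
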